IV	Intravenous
IWRS	Interactive Web Response System
LFT	Liver function test
M stage	Metastatic stage (M1 indicates presence of distant metastases)
Mb	Megabase
MedDRA	Medical Dictionary for Regulatory Activities
mPR	Major pathologic response
MRI	Magnetic resonance imaging
N stage	Nodal stage
NAb	Neutralizing antibody
NCI-CTCAE	National Cancer Institute-Common Terminology Criteria for Adverse Events
NSCLC	Non-small cell lung cancer

Abbreviation	Definition of Term
ORR	Objective response rate
OS	Overall survival
PBMC	Peripheral blood mononuclear cells
pCR	Pathologic complete response
PD	Progression of disease
PD-1	Programmed death-1 (receptor)
PD-L1	Programmed death ligand 1
PD-L2	Programmed death ligand 2
PET	Positron emission tomography
PK	Pharmacokinetic
PR	Partial response
PT	Prothrombin time
Q2W	Every 2 weeks
Q3W	Every 3 weeks
R0	Microscopically margin-negative resection; no gross or microscopic tumor remaining in the primary tumor bed
R1	Removal of all macroscopic disease; microscopic margins are positive for tumor
R2	Gross disease after surgery; macroscopically positive surgical margins
RECIST	Response Evaluation Criteria in Solid Tumors
Regeneron	Regeneron Pharmaceuticals, Inc.
SAE	Serious adverse event
SAF	Safety analysis set
SAP	Statistical analysis plan
SAS	Statistical Analysis System
SD	Stable disease
SOC	System organ class
SPT	Second primary tumor
SUSAR	Suspected unexpected serious adverse reaction
T stage	Tumor stage
TEAE	Treatment-emergent adverse event
TMB	Tumor mutation burden
TNM	Tumor, Node, Metastasis
TSH	Thyroid-stimulating hormone
UICC	Union for International Cancer Control
ULN	Upper limit of normal

Abbreviation	Definition of Term
US	United States
USPI	United States Prescribing Information
UV	Ultraviolet
WOCBP	Women of childbearing potential

TABLE OF CONTENTS

LIST OF ABBREVIATIONS AND DEFINITIONS OF TERMS.....	2
CLINICAL STUDY PROTOCOL SYNOPSIS.....	13
1. INTRODUCTION.....	19
1.1. Background on Cutaneous Squamous Cell Carcinoma.....	19
1.2. Background on Cemiplimab.....	19
1.3. Efficacy of Cemiplimab in Advanced CSCC.....	20
2. STUDY OBJECTIVES.....	20
2.1. Primary Objective.....	20
2.2. Secondary Objectives.....	20
2.3. Exploratory Objectives.....	21
3. HYPOTHESIS AND RATIONALE.....	21
3.1. Hypothesis.....	21
3.2. Rationale.....	21
3.2.1. Rationale for Dose Selection.....	21
3.2.2. Rationale for Neoadjuvant Cemiplimab in Locally Advanced Patients with CSCC Who Are Candidates for Surgery.....	21

12.2.1.	Monitoring of Study Sites	78
12.2.2.	Source Document Requirements	78
12.2.3.	Case Report Form Requirements	79
12.3.	Audits and Inspections	79
12.4.	Study Documentation	79
12.4.1.	Certification of Accuracy of Data	79
12.4.2.	Retention of Records	80
13.	ETHICAL AND REGULATORY CONSIDERATIONS	80
13.1.	Good Clinical Practice Statement	80
13.2.	Informed Consent	80
13.3.	Patients Confidentiality and Data Protection	81
13.4.	Institutional Review Board/Ethics Committee	81
13.5.	Clinical Study Data Transparency	81
14.	PROTOCOL AMENDMENTS	82

15.	PREMATURE TERMINATION OF THE STUDY OR CLOSE-OUT OF A SITE.....	82
15.1.	Premature Termination of the Study.....	82
15.2.	Close-out of a Site	82
16.	CONFIDENTIALITY	82
17.	FINANCING AND INSURANCE.....	83
18.	PUBLICATION POLICY	83
19.	REFERENCES	84
20.	INVESTIGATOR’S AGREEMENT.....	88
	SIGNATURE OF SPONSOR’S RESPONSIBLE OFFICERS	89

LIST OF TABLES

Table 1:	General Guidelines for Management of Treatment-Related AEs.....	40
Table 2:	Schedule of Events for Screening, Neoadjuvant Cemiplimab, and Surgery (Part 1 of the Study).....	47
Table 3:	Schedule of Events for Adjuvant Cemiplimab (Part 2 of the Study)	50
Table 4:	Schedule of Events for Follow-Up After Part 2 of the Study.....	52
Table 5:	Grading System for Adverse Events Not Listed in NCI-CTCAE	69
Table 6:	The 95% Binomial Exact Confidence Intervals for Observed pCR with a Sample Size of 76 Patients	72

LIST OF FIGURES

Figure 1:	Study Flow Diagram.....	31
-----------	-------------------------	----

LIST OF APPENDICES

Appendix 1.	Eastern Cooperative Oncology Group Criteria	90
Appendix 2.	Guidelines for Management of Selected Immune-Related Adverse Events	91
Appendix 3.	Guidelines For Exploratory Biopsies	101
Appendix 4.	Response Evaluation Criteria in Solid Tumors: RECIST Guideline (Version 1.1).....	102
Appendix 5.	Digital Photographic Procedures.....	107

CLINICAL STUDY PROTOCOL SYNOPSIS

Title	A Phase 2 Study of Neoadjuvant Cemiplimab for Stage II to IV (M0) Cutaneous Squamous Cell Carcinoma (CSCC)
Site Location(s)	Approximately 20 sites in North America, Europe, and Asia-Pacific
Principal Investigator	[name], FACS
Objective(s)	
Primary Objective	To evaluate the efficacy of neoadjuvant cemiplimab as measured by pathologic complete response (pCR) rate per independent central pathology review.
Secondary Objectives	
The secondary objectives of the study are:
 
 • To evaluate the efficacy of neoadjuvant cemiplimab on measures of disease response, including: 
 – Major pathologic response (mPR) rate per independent central pathology review – pCR rate and mPR rate per local pathology review – Objective response rate (ORR) prior to surgery, according to local assessment using RECIST 1.1 • To evaluate the efficacy of neoadjuvant cemiplimab on event free survival (EFS), disease free survival (DFS), and overall survival (OS) • To evaluate the safety profile of neoadjuvant cemiplimab • To assess change in surgical plan (ablative and reconstructive procedures) from the screening period to definitive surgery, both according to investigator review and independent surgical expert review • To assess change in post-surgical management plan (radiation, chemoradiation, or observation) from the screening period to post-surgery pathology review, both according to investigator review and independent surgical expert review
Exploratory Objectives	
The exploratory objectives of the study are:
 
 • To explore baseline tumor markers for associations with treatment responses, peripheral and tumor measures associated with cemiplimab mechanism of action and discovery of other potential predictive markers of efficacy or safety • To describe patterns of failure (locoregional versus distant) in patients who experience disease recurrence • To evaluate the cost implication due to changes in surgical plan during screening period versus actual surgical procedure performed

- To evaluate the cost implication due to changes in post-surgical management plan during screening period versus actual post-surgical management
- To assess the immunogenicity of cemiplimab
- To assess health-related quality of life in patients with CSCC who receive neoadjuvant cemiplimab

Study Design

This is a single-arm, open label, multicenter phase 2 study for patients with stage II to IV (M0) CSCC who are candidates for surgery, but who have an increased risk of recurrence and/or risk of disfigurement or loss of function. Patients with stage III or IV (M0) CSCC of the head/neck, extremity, or trunk are eligible, as well as selected patients with stage II CSCC (≥ 3 cm longest diameter in an aesthetically sensitive region).

The study consists of 2 parts:

- Part 1 (neoadjuvant): A screening period of up to 28 days, a treatment period of up to 12 weeks, and surgery after 12 weeks of treatment. Part 1 of the study supports the primary endpoint
- Part 2 (adjuvant): Optional post-surgery cemiplimab treatment for up to 48 weeks (or radiation therapy, or observation only, at investigator discretion)

Study Part 1 (Neoadjuvant)

Patients with stage II to IV (M0) CSCC with planned surgery and who fulfill the eligibility criteria will receive cemiplimab 350 mg intravenously (IV) every 3 weeks (Q3W) for up to 12 weeks (up to 4 doses), or until unacceptable toxicity, disease progression, or withdrawal of consent. Patients will be evaluated in clinic prior to each dose and will undergo tumor response imaging assessment prior to receiving the third dose of cemiplimab (day 43 \pm 3) and prior to surgery (day 85). The window for surgery is from day 75 through day 100. If a patient meets criteria to discontinue cemiplimab during the 12-week neoadjuvant period, the treating physician may divert the patient to surgery at an earlier time.

Following surgical tumor resection, the primary endpoint (pCR rate) will be assessed by an independent central pathology review committee.

Study Part 2 (Adjuvant)

Patients will have the option to receive adjuvant cemiplimab treatment (350 mg IV Q3W) following surgery for up to 48 weeks (up to 16 doses) or until unacceptable toxicity, disease recurrence, or withdrawal of consent. The first dose of adjuvant treatment will occur 3 weeks (± 3 days) after the end of treatment in Part 1 (EOT1). At the investigator's discretion, patients may alternatively receive adjuvant radiation therapy (concurrent or subsequent cemiplimab treatment not allowed) or enter an observation-only period.

During Part 2 of the study, patients will be evaluated in clinic every 15 weeks. Patients receiving adjuvant cemiplimab will undergo complete assessments as described in the schedule of events, while patients who do not receive adjuvant cemiplimab will only undergo imaging assessments following a parallel schedule.

	Follow-Up
	Follow-up will begin after a patient has completed Part 1 and Part 2 of the study without disease progression (pre-surgery) or disease recurrence (post-surgery). Patients will be evaluated in clinic for up to 3 additional years.
Study Duration	
Part 1: Up to 12 weeks
 
Part 2: Up to 48 weeks
 
Follow-up: Up to 3 years. Patients will be followed until disease recurrence or end of study, whichever occurs first.

End of Study Definition	The end of study is defined as the last visit of the last patient.
Population	
Sample Size:	Approximately 76 patients will be enrolled.
Target Population:	
The target population will consist of adult patients with stage III to IV (M0) CSCC of the head/neck, extremity, or trunk, and selected patients with stage II CSCC, for whom surgery would be recommended in routine clinical practice.
 
Patient criteria include, but are not limited to, the following:
 
 • No prior radiation therapy for CSCC • At least one lesion that is measurable by RECIST 1.1 • For stage II patients, lesion must be ≥ 3 cm at the longest diameter
Treatment(s)	
Study Drug	Cemiplimab 50 mg/mL supplied as a sterile liquid in single-use glass vials.
Dose/Route/Schedule:	350 mg IV infusion over 30 minutes (± 10 minutes) Q3W.
Endpoint(s)	
Primary:	The primary endpoint is pCR rate assessed by independent central pathology review.
Secondary:	
The secondary endpoints are:
 
 • Major pathologic response (mPR) rate assessed by independent central pathology review • pCR rate and mPR rate assessed by local pathology review • ORR prior to surgery, according to investigator assessment using RECIST 1.1 • Event free survival (EFS) • Disease free survival (DFS) • Overall survival (OS) • Safety and tolerability as measured by the incidence of adverse events (AEs), serious adverse events (SAEs), deaths, and laboratory abnormalities

- Change in surgical plan in the screening period versus actual surgery after neoadjuvant cemiplimab
- Change in post-surgical management plan in the screening period versus actual post-surgical management

Exploratory:

The exploratory endpoints are:

- Patterns of failure in patients with local, regional, or distant disease recurrence as measured by descriptive statistics
- Change in estimated costs due to change in surgical plan during screening period versus actual surgical procedure performed after neoadjuvant cemiplimab
- Change in estimated costs due to the change in post-surgical management plan during screening period versus actual post-surgical management
- Incidence of anti-drug antibody (ADA) for cemiplimab
- Health-related quality of life, as assessed using the European Organization for Research and Treatment of Cancer Quality of Life Questionnaire-Core 30 (EORTC QLQ-C30)

Procedures and Assessments**Procedures Performed Only at Screening/Baseline**

Patients will undergo screening for hepatitis B virus (HBV), hepatitis C virus (HCV), and human immunodeficiency virus (HIV), and height measurement only at the screening/baseline visit for the sole purpose of determining study eligibility or characterizing the baseline population. Women of childbearing potential will additionally undergo serum β -human chorionic gonadotropin (HCG) testing. During screening, medical/oncological history is obtained.

Efficacy Procedures

Surgically resected tumors will be evaluated for pathologic response by an independent central pathology review committee.

Changes in surgical plan and post-surgical management plan will be evaluated both locally and by an independent surgical committee. Assessment parameters include, but are not limited to, description of planned/actual surgery, length of hospital stay, whether surgery was more/less extensive than planned, and planned/actual adjuvant radiation therapy.

Patients will undergo radiologic imaging assessments for tumor response (neoadjuvant portion of the study) and for disease recurrence (adjuvant portion of the study and follow-up). Imaging of externally visible lesions will be supplemented with digital medical photography. Digital photography is mandatory at baseline and prior to surgery in Part 1 and optional for all other imaging visits in the study.

Biopsy of tumors will be performed when feasible to obtain histologic or cytologic evidence of disease recurrence or evidence of a second primary tumor (SPT). For recurrent lesions, the pattern of failure will be assessed, with recurrence defined as ≥ 1 lesion that can be categorized as local, regional, or distant recurrence.

Safety Procedures

Safety and tolerability of cemiplimab will be evaluated via adverse event (AE) capturing, physical examination (complete or limited), weight, 12-lead electrocardiogram (ECG), vital sign assessments, and laboratory testing, including hematology, blood chemistry, and urinalysis.

Statistical Plan**Statistical Hypothesis**

The primary endpoint is pCR by independent central review. The following null and alternative hypotheses will be tested for the primary efficacy endpoint:

H0: pCR rate = 25%

Ha: pCR rate \neq 25%

Justification of Sample Size

Seventy-two (72) patients will be required to provide 90% power to reject the null hypothesis (pCR rate = 25%) at a 2-sided significance level of 0.05 if the true pCR rate is 44%. The sample size will be further increased by 5% to account for patients who prematurely withdraw from the study (total sample size of approximately 76 patients).

The non-clinically meaningful pCR rate of 25% will be excluded using the lower limit of 95% exact confidence interval (CI) if the observed pCR rate is 36.8% or more.

Patients who discontinue treatment early and/or withdraw will not be replaced, and the results will be analyzed by intention-to-treat. To ensure meaningful representation of stage III/IV (M0) patients, enrollment of stage II patients will be capped at 25.

Interim Analysis

No interim analysis is planned for the primary endpoint. After all patients have completed Part 1 of the study, an interim clinical study report (CSR) may be written to describe the analysis results for the primary endpoint. The final CSR will be written to describe the final results of the study, after all patients have had the opportunity to complete Part 2 of the study and post-treatment follow-up.

Efficacy Analysis Methods**Primary efficacy analysis:**

Pathologic complete response (pCR) rate per independent central pathology review, along with the 95% exact confidence interval, will be calculated using the Clopper-Pearson method.

Secondary efficacy analysis:

Pathologic complete response (pCR) rate per local pathology review, mPR rate per independent central pathology review, mPR rate per local pathology review, and ORR prior to surgery per investigator assessment, along with 95% exact confidence intervals, will be calculated using the Clopper-Pearson method.

Event free survival (EFS), DFS, and OS will be summarized using the Kaplan-Meier method, and Kaplan-Meier curves will be generated. Descriptive statistics will be used for time-to-event endpoints.

Change in planned surgery will be summarized descriptively and will be listed. The proportion of patients for whom the surgical management plan (at time of screening) differed from the actual surgery after neoadjuvant therapy will be summarized both by investigator assessment and independent surgical expert committee.

Change in planned post-surgical management will be summarized descriptively and will be listed. The proportion of patients for whom radiation therapy (or chemoradiation) was planned during screening but not actually administered after neoadjuvant cemiplimab and surgery will be summarized.

Safety Analysis Methods

Treatment-emergent adverse events (TEAEs), SAEs, and adverse events of special interest (AESIs) will be summarized using descriptive statistics.

Treatment-emergent AEs (TEAEs) are defined as AEs that developed or worsened during the on-treatment period and any treatment-related AEs that occur during the post-treatment period but prior to patients receiving their first dose of cemiplimab as adjuvant therapy or another anticancer systemic therapy.

Adverse events (AEs) during adjuvant cemiplimab will be summarized separately from AEs emerging in the neoadjuvant period. AEs will be collected from the date of first dose of adjuvant cemiplimab up to 90 days following the last dose. Additionally, any treatment-related AEs identified more than 90 days following the last dose will be captured.

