2.2. Secondary Objectives

The secondary objectives of the study are:

- To evaluate the efficacy of neoadjuvant cemiplimab on measures of disease response, including:
 - Major pathologic response (mPR) rate per independent central pathology review
 - pCR rate and mPR rate per local pathology review
 - ORR prior to surgery, according to local assessment using RECIST 1.1
- To evaluate the efficacy of neoadjuvant cemiplimab on event free survival (EFS), disease free survival (DFS), and overall survival (OS)
- To evaluate the safety profile of neoadjuvant cemiplimab
- To assess change in surgical plan (ablative and reconstructive procedures) from the screening period to definitive surgery, both according to investigator review and independent surgical expert review
- To assess change in post-surgical management plan (radiation, chemoradiation, or observation) from the screening period to post-surgery pathology review, both according to investigator review and independent surgical expert review

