5.2. Efficacy Variables

5.2.1. Disease Response and Disease Recurrence

Disease response will be assessed by surgical pathology using pCR and mPR. Pathologic complete response (pCR) is defined as absence of viable cancer cells in the surgical pathology sample. Major pathologic response (mPR) is defined as $\leq 10\%$ viable cancer cells in the surgical pathology sample, in patients who have not achieved pCR. Procedures to assess pCR and mPR in the surgical pathology sample after neoadjuvant therapy are not described in this protocol but will be described in a separate charter.

Objective response rate (ORR) will be assessed by the investigator using RECIST 1.1 (Eisenhauer, 2009)(Appendix 4). Procedures for assessing ORR are outlined in Section 9.2.2.3. Confirmation of complete or partial response is not required.

Event free survival (EFS) is defined as time from first dose of neoadjuvant cemiplimab to any of the following events: progression of disease that precludes surgery, inability to undergo complete resection (R0 or R1), disease recurrence (local, regional, or distant) for patients who undergo complete resection (R0 or R1), or death due to any cause.

Disease free survival (DFS) is defined as time from surgery to first recurrence (local, regional, or distant) or death due to any cause, for patients who are free of disease (R0 or R1 resection) at completion of surgery. Patterns of failure in patients with local, regional, or distant disease recurrence will be assessed by descriptive analysis according to the procedures outlined in Section 9.2.2.5 and Section 9.2.2.6.

Overall survival (OS) will be measured as time from first dose of neoadjuvant cemiplimab to death due to any cause.

5.2.2. Changes in Planned Surgery and Post-Surgical Management (Per Investigator and Per Independent Review)

Electronic case report forms (eCRFs) will capture what the management plan would be for surgery and post-surgical management if the patient were not enrolled in a clinical trial, as well as the actual surgery that was performed and the actual post-surgical management.

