5.2.2.2. Actual Management on the Study

The following information will be collected in additional pages of the eCRF:

- Was the post-surgical treatment plan formulated at a multidisciplinary tumor board after surgery (including surgery, radiation oncology, and medical oncology)? (Yes/No)
- Description of surgical resection
Note: eCRF pages will provide options for ablative procedures commonly performed in this patient population
- Description of reconstruction (if applicable)
Note: eCRF pages will provide options for ablative procedures commonly performed in this patient population
- What was the length of inpatient hospital stay after surgery? (Days)
- In the opinion of the investigator, was surgery after neoadjuvant cemiplimab unchanged, less extensive, or more extensive than what was planned during screening?
Note: If more extensive or less extensive than planned during screening, additional details will be requested in eCRF
- For patients who receive adjuvant radiation therapy or chemoradiation after surgery, the following treatment summary data will be captured in the eCRF:
 - Anatomic site of radiation therapy
 - Radiation therapy technique (eg, intensity-modulated radiotherapy)
 - Total radiation therapy dose
 - Total number of fractions
 - Fractionation schedule (eg, daily treatment at 5 days per week)

- Treatment interruptions (if any)
- Start date and end date
- If concurrent chemotherapy is administered with radiation therapy: name of chemotherapy drug, days and doses of administration

For independent review, variables to assess changes in planned surgery and post-surgical management will be described in a separate charter. Independent review by surgical committee will not be performed in real time and will not influence clinical decision making for study participants. The sponsor will be blinded to results of independent review until after data cut for the primary endpoint.

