9.1.6. Visit Schedule for Patients Who Receive Adjuvant Radiation Therapy or Observation Only

After surgery, management options include adjuvant cemiplimab, adjuvant radiation therapy, or observation only. A patient who receives adjuvant radiation therapy will not receive adjuvant cemiplimab (neither sequentially nor concurrently) during the study.

Patients who undergo adjuvant radiation therapy or enter observation only during Part 2 of the study will be assessed by imaging only, at week 15 (± 10 days), week 30 (± 10 days), and week 48 (± 10 days) (corresponding to the equivalent EOT2 visit for patients receiving cemiplimab). Week 0 is defined as 3 weeks (± 3 days) after the EOT1 visit. Other assessments listed in [Table 3](#) are not required for a patient who receives adjuvant radiation therapy or observation only. However, biopsy should be attempted for all patients in the event of suspected recurrence or suspected SPT as described in [Section 9.2.2.7](#).

Patients who complete the week 48 evaluation visit without disease recurrence will enter follow-up, in which they undergo imaging assessments every 4 months for the first 2 years and every 6 months for the third year.

Details regarding the adjuvant therapy received by an individual patient will be reported in the eCRF (Section 12).

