5.6.2. Analysis of Secondary Efficacy Variables

The pCR rate per local pathology review, mPR rate per independent central pathology review, mPR rate per local pathology review, and ORR prior to surgery per investigator assessment will be summarized and corresponding two-sided 95% exact CIs will be calculated by Clopper-Pearson method (Clopper, 1934).

Percent residual viable tumor (%RVT) will be summarized descriptively.

Combined efficacy based on both ORR per RECIST 1.1 and pCR and mPR per pathology review may be explored.

The distribution of EFS, DFS, and OS will be estimated using the Kaplan-Meier method. The median EFS, median DFS, and median OS along with 95% CIs will be presented and Kaplan-Meier estimates with 2-sided 95% CIs at specific time points will be summarized. The Kaplan Meier curves will be presented.

As regards the DFS endpoint, a descriptive summary will be performed for each subgroup of patients who receive adjuvant cemiplimab, adjuvant radiation therapy, and observation after surgery.

Change in planned surgery will be summarized descriptively. The proportion of patients for whom the surgical management plan (at time of screening) differed from the actual surgery after neoadjuvant therapy will be summarized both by investigator assessment and independent surgical expert committee.

Change in planned post-surgical management will be summarized descriptively. The proportion of patients for whom radiation therapy (or chemoradiation) was planned during screening but not actually administered after neoadjuvant cemiplimab and surgery will be summarized.

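### The only named statistic for change in post-surgical management counts radiation planned but not given, with no counterpart for radiation given but not planned

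*Protocol*

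**What the plan says.** The secondary objective in Protocol 2.2 is "To assess change in post-surgical management plan (radiation, chemoradiation, or observation) from the screening period to post-surgery pathology review". Neither it nor the matching endpoint in Protocol 4.2 states a direction.

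The analysis text is in three places: the Synopsis (Efficacy Analysis Methods), Protocol 11.5.3.2 and SAP 5.6.2. Each names a single proportion, that of patients for whom "radiation therapy (or chemoradiation) was planned during screening but not actually administered after neoadjuvant cemiplimab and surgery". The sentence before it is general. The protocol has "Change in planned post-surgical management will be summarized descriptively and will be listed"; the SAP has "Change in planned post-surgical management will be summarized descriptively" and does not repeat the listing.

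The surgery endpoint is treated differently in the same places. Its statistic is "The proportion of patients for whom the surgical management plan (at time of screening) differed from the actual surgery after neoadjuvant therapy", which counts a change in either direction.

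The screening entry is a hypothetical. Under Protocol 5.2.2 the eCRF records "what the management plan would be for surgery and post-surgical management if the patient were not enrolled in a clinical trial". Actual radiation is also recorded (Protocol 5.2.2.2): "For patients who receive adjuvant radiation therapy or chemoradiation after surgery, the following treatment summary data will be captured in the eCRF".

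Part 2 offers adjuvant cemiplimab, radiation or observation. Protocol 9.1.6 makes the first two exclusive: "A patient who receives adjuvant radiation therapy will not receive adjuvant cemiplimab (neither sequentially nor concurrently) during the study".

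**The concern.** A forecast made before surgery will sometimes be wrong. Protocol 3.2.3 ties guideline recommendations for radiation to positive margins and extensive perineural invasion and, in the European guidelines, to multiple involved nodes or extracapsular involvement after node dissection. Part of this is known only from the resected specimen. Some patients planned for radiation will not need it, and some planned for observation will, with or without a drug effect. The named proportion counts the first group and has no place for the second.

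Substitution acts in the same direction. The screening plan offers radiation, chemoradiation or observation (Protocol 5.2.2.1), but after surgery there is a further option that excludes radiation. A patient planned for radiation who takes adjuvant cemiplimab is counted as planned but not given, however the tumour responded before surgery.

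Two things are at stake. Protocol 3.3.1 lists avoidance of postoperative radiation as a potential benefit, and this proportion is the number a reader would take as evidence for it. Protocol 3.3.2 calls loss of the chance of curative resection through progression the fundamental risk. A patient planned for observation who progresses, is resected and then receives radiation does not appear in the statistic. The study is single-arm, so no comparison group calibrates the figure.

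**Working it through.** **The plan's own figure.** There is none to reproduce. The documents give no expected rate, precision or threshold for this endpoint. N = 76 is the planned enrolment (Protocol 7.1). The rates below are assumptions.

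**Notation.**
- π = share of patients with radiation or chemoradiation planned at screening
- a = probability that it is not given when planned
- b = probability that it is given when not planned

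Then:
- named statistic = π·a
- reverse flow = (1 − π)·b
- net change = π·a − (1 − π)·b

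**Boundary case.** If every planned course is given, a = 0 and the statistic is 0. For any a above 0 it is positive. It does not depend on b.

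**Symmetric forecast error, overall radiation rate unchanged.** Set b = π·a/(1 − π), so the net is 0 by construction. At π = 0.50 and a = 0.20:
- b = 0.50 × 0.20 / 0.50 = 0.20
- named statistic = 0.50 × 0.20 = 10%, or 7.6 of 76
- reverse flow = 0.50 × 0.20 = 10%, or 7.6 of 76
- net = 0

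The named statistic over a range of assumptions, with net 0 in every cell:

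| π | a = 0.10 | a = 0.20 | a = 0.30 |
|---|---|---|---|
| 0.30 | 3% (2.3 patients) | 6% (4.6) | 9% (6.8) |
| 0.50 | 5% (3.8) | 10% (7.6) | 15% (11.4) |
| 0.70 | 7% (5.3) | 14% (10.6) | 21% (16.0) |

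The chance that at least one patient is counted is 1 − (1 − π·a)^76. That is 0.90 at π·a = 0.03 and at least 0.98 in every other cell. The bottom right cell is extreme: it needs b = 0.70 × 0.30 / 0.30 = 0.70, so that 70% of patients with no radiation planned receive it.

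**Substitution by adjuvant cemiplimab.** Let s be the share of planned-radiation patients who take adjuvant cemiplimab instead, with no other change of plan. The statistic is π·s. At π = 0.50:
- s = 0.2: 10% (7.6 patients)
- s = 0.4: 20% (15.2)
- s = 0.6: 30% (22.8)

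There is no reverse flow here, so the net difference takes the same values. The net does not remove this route.

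**Denominator.** SAP 5.6.2 does not say whether the percentage is of the full analysis set or of patients with radiation planned. At π = 0.50 and a = 0.20 these give 10% and 20%. The full analysis set is all dosed patients (SAP 3.1), including any who never reach surgery. SAP 6.3 leaves patients with missing data out of percentages but does not say whether a patient without surgery counts as missing.

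**Precision of the net difference.** With both discordant proportions at 10%, the Wald standard error is √[(0.10 + 0.10 − 0²)/76] = 0.0513. The 95% half-width is 1.96 × 0.0513 = 0.101, about 10 percentage points.

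**The case against.** The strongest reply is that a reader might infer that the plan discards radiation given but not planned, and it does not. The general sentence promises a descriptive summary of change in post-surgical management. SAP 5 (and Protocol 11.5) says categorical data are shown as frequencies and percentages by category, so a move from observation to radiation could appear there, and in the protocol's listing. The exploratory change in cost (Protocol 5.2.2.3; SAP 4.4.3) also moves both ways, because planned observation is costed at zero and adjuvant therapy received is costed. The variables for independent review are in a charter that is not among these documents. All of this stands. What remains is that the summary has no stated layout and the one quantity fixed in advance is the favourable direction. The cost measure does not count patients who received radiation.

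A second reply is that the effect is conditional and its size assumed. This also stands. Nodal and perineural involvement enter the staging (Protocol 3.2.4), so some reasons for radiation can be known at screening, and forecasts may be better than the larger values of a suggest.

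A third reply is that the net difference is no cleaner. A reader might infer that it separates a drug effect from forecast error. It does so only if the errors are equal in both directions, and the substitution figures show that it can be well above zero with no neoadjuvant effect. This limits what may be claimed from the net. It does not support reporting one direction alone.

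Finally, the endpoint is descriptive and carries no test or multiplicity control (Protocol 11.5.4; SAP 5.6.4). That is correct.

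**Conclusion.** The point holds in a limited form. The only pre-specified statistic for a non-directional objective runs in one direction and cannot show an increase in radiation. Forecasts revised after pathology and substitution by adjuvant cemiplimab both raise it, whatever the neoadjuvant effect. In the illustration (50% planned, 20% of those not given, equal reverse flow) it reads 10%, or 7.6 of 76, with a net change of 0. Those three inputs are assumptions, and the zero net follows from the third.

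A reader might go further and say that the figure must show radiation avoided even without a drug effect. The documents do not support that: if all planned courses are given it is 0, and no rate of disagreement is stated. Nor do they support saying that reverse cases are lost, because they are collected and may be summarised. The primary endpoint, sample size and error rates are unaffected. The change is worth making before the analysis because it replaces a one-sided figure with a balanced one from data already planned.

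**What to change.** In SAP 5.6.2:
- Specify a planned-by-actual table of radiation or chemoradiation (yes/no by yes/no) on a stated denominator, with patients who had no surgery shown separately.
- Report both discordant proportions, planned but not given and given but not planned, and the paired net difference with a 95% CI.
- Break the table down by post-surgical option received: adjuvant cemiplimab, radiation or observation.
- State that the one-way proportion alone is not to be described as radiation avoided. State also that the net difference cancels only symmetric forecast error and does not estimate the neoadjuvant drug effect.

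The protocol text can stay, since its proportion becomes one cell of the table. The eCRF already collects planned and actual management (Protocol 5.2.2.1 and 5.2.2.2). The cost is a few SAP sentences, one more table and probably a less favourable figure.
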